## **B. Background and Significance**

Amyotrophic Lateral Sclerosis (ALS) is a devastating progressive neurodegenerative disease. ALS affects people of all ages and both sexes with a reported annual incidence of 1 in 100,000. There are an estimated 30,000 Americans who suffer from ALS at any given time. With no effective therapy, the average lifespan for patients is 2-5 years (2). At present the only FDA approved drug to treat ALS is Riluzole, a drug with several modes of action including NMDA receptor antagonism and Radicava, a drug thought to act as a free radical scavenger and prevent oxidative stress damage to neurons. However, the benefits of Riluzole are marginal, with the pivotal studies showing that Riluzole prolonged life by only three months and did not significantly delay the loss of functional milestones. Radicava may slow disease progression in a subset of patients with a particular clinical presentation, but more clinical trial data is required to evaluate Radicava's effectiveness in all ALS patients. Thus, a more effective therapy is desperately needed for this universally fatal disease.

Although the most visible symptom in (ALS) is progressive weakness and loss of muscle, approximately half of all people with ALS also exhibit some symptoms of cognitive impairment and associated behavioral symptoms (*frontotemporal dysfunction*) (3). FTD is caused by *frontotemporal lobar degeneration* (FTLD), a type of progressive deterioration in the frontal and temporal lobes of the brain, which is responsible for cognitive function. While the neuromuscular deficits associated with ALS have been well characterized, screening methods for detecting behavioral and cognitive impairment have been very limited. In addition, few studies

have really examined ways to try to improve these neuropsychiatric effects which often have major impacts upon a patient and their family's quality of life.

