## **Results of Open Label Trial**

Memantine, an FDA approved agent for the treatment of Alzheimer's disease, has been thought to reduce the effects of glutamate mediated excitotoxicity (19). It may also inhibit and reverse the abnormal hyperphosphorylation of tau, which leads to its sequestration in neuronal intracellular inclusions (20). In addition, Memantine has been shown to prolong survival in a transgenic mouse model of amyotrophic lateral sclerosis (21). Based on the potential for Memantine to alter the course of the disease in ALS patients, Phoenix Neurological Associates conducted a 20 patient, open label pilot trial of Memantine given at 10 mg bid, in patients taking Riluzole. The data suggested that Memantine might have significant clinical benefit in patients with ALS.

19 patients completed more than 3 months of therapy, 16 patients completed 6 months of therapy and 12 patients completed the entire 18 months of the study. Patients were evaluated based on the number of points lost per month on the ALS Functional Rating Scale - Revised (ALSFRS-R). The ALSFRS-R is a validated measure of ALS disease progression and is a predictor of survival that is typically used as an accepted outcome measure in ALS clinical trials (27, 28). As this was an open-label trial, patients were compared to historical controls and a subset of patients were compared to their pre-study rate of progression. Numerous placebo-controlled studies in ALS have shown that patients on Riluzole, or on no therapy, lose on average -0.9 ALSFRS-R points per month (29).

[figure not shown]
A linear mixed effects model was used to compare rates of decline for the 20 patients taking Memantine with 415 placebo patients from previous clinical trials. This natural history model (from 8 previous clinical trials) estimated a slope of -0.89 (95% CI -0.95 to -0.83) for placebo and -0.55 (95% CI -0.95 to -0.15) for Memantine treated patients (two-sided  $p=0.10$  for the treatment effect). This represents a 38% reduction in slope in this small sample.

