## **C. Sample Size, Statistical Methods, and Power Calculation**

### *Sample size*

90 patients will be randomized in a 2:1 ratio to either Memantine, 20 mg BID or placebo. The active and placebo will be over encapsulated by the research pharmacy at the University of Iowa Research Pharmacy. Medication will be dispensed at 10 mg and placebo kits that are blinded to the investigator and the patient. After the patient fulfills screening criteria, data entered into the database, and their screening visit is monitored remotely, the patient will be randomized using a predetermined randomization formula. KUMC will provide the site with proper kit numbers for each randomized patient. All randomized patients will be instructed to take one capsules once a day for the first two weeks from a blinded bottle that contains the 10 mg capsules or matching placebo. At week three, patients will be instructed to take one capsule twice a day. At week five, patients will be instructed to take one capsule in the morning and 2 capsules in the evening. At week seven, patients will be instructed to take two capsules twice a day. Patients will remain on this dose for the remainder of the study; unless they cannot tolerate the dose. If this is the case, they will follow the proper dosing taper (see dosing reduction/discontinuation section).

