### *Statistical Methods*

The primary comparison for efficacy will be based on a linear mixed effects (lme) model fit to the ALSFRS-R data for the 90 patients followed over 36 weeks. The model will be used to calculate fixed effects for intercept, placebo slope (rate of decline of ALSFRS-R) and change in slope for those treated with Memantine. Random effects included are for individual patient variation in intercept, slope and random error at each time point. The test for treatment effect is based on the change in slope due to treatment, as estimated by the model. Testing for significance is two-sided at a 10% level of significance. Analysis is limited to patients who receive at least one treatment dose and have at least 2 measurements (one at baseline and one after treatment). Deaths are treated the same as drop-outs. This model weighs each patient inversely by his estimated variance so that patients with missing values receive less weight than those with complete data.

We will also attempt to enrich the placebo group with historical controls with matching patients from the historical placebo database of 715 patients added to the 30 placebo patients from this trial. The historical controls will be selected to have same entry criteria as patients in this trial. There will be no patient-by-patient matching. We will first test whether the 30 patients from this trial differ from those in the historical database (using the same model with a term added to identify source: historical or contemporary). If this test finds that the two placebo groups differ, historical control will not be added and the combined placebo vs treated test will not be conducted. If the placebo control sets do not differ, the lme model described above will be fit to the combined data.

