#### *Statistical Power*

We used data from our historical placebo to estimate power for both the test that uses only patients enrolled in the trial and the test where historical placebo is added. To accomplish this we first randomly sampled 75 placebos from our database. The first 30 are assigned as placebo and their ALSFRS-R values are unchanged. The remaining 60 have their slopes reduced by a fixed percentage of their lme estimated slope and the random error is added back in to simulate real measurements. Next, we test for a treatment effect in the simulated dataset of 90. The simulated data are then combined with the remaining (unsampled) placebo and tested for difference in the placebo subgroups. If this test is not significant (at two-sided  $p<0.05$ ), the combined data are tested for a treatment effect. This procedure was carried out 1000 times, noting the p-values from each simulation. Power was estimated by counting the number of times p-values were less than 0.1 (two-sided test).

These simulations with a treatment effect set to 40% show that with 90 patients at a 2:1 ratio of Memantine to placebo, power was 82% for the test that uses only the 90 patients simulated to be in the trial. Adding historical placebo boosted the power to over 90%.

Because there is a great deal of clinical variability among patients with ALS the major drawback to this study is its small size. A previous study looking at 60 ALS patients performed by Carvalho et al, found no significant improvement in patients randomized to 10 mg BID of Memantine compared to placebo (30). This contradicts the data from our pilot study in which patients' rate of progression was compared both to historical controls and their own baseline rate

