### **2. Eligibility**

#### Inclusion Criteria

1. Age 18-85
2. Male or Female
3. Clinically definite, probable, probable lab-supported, or possible ALS by El Escorial criteria
4. ALSFRS-R > 25
5. Must be willing to undergo longitudinal blood draws for biomarker analysis
6. Availability and willingness to complete the study
7. Capable of providing informed consent and complying with trial procedures
8. If patients are taking Riluzole and/or Radicava, they must be on a stable dose for at least thirty days prior to the baseline.

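### Combined test with historical placebo neither aligns nor adjusts for Radicava use; if use is lower in the pool, most of any Radicava slowing is counted as memantine effect

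*Combined protocol and SAP*

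**What the plan says.** The primary analysis is confined to the randomised patients: "The primary comparison for efficacy will be based on a linear mixed effects (lme) model fit to the ALSFRS-R data for the 90 patients". Allocation is 2:1, so 60 memantine and 30 placebo, and "Testing for significance is two-sided at a 10% level of significance".

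Statistical Methods then describes a further test that adds patients from a 715-patient historical placebo database to the 30 concurrent placebo patients. On comparability it says "The historical controls will be selected to have same entry criteria as patients in this trial", and it rules out individual matching. A source term is tested first, and pooling is dropped if the two placebo groups differ. The 5% two-sided level for that source test appears only in the simulation under Statistical Power. The listed fixed effects are intercept, placebo slope and the change in slope on memantine.

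On background therapy, Inclusion Criteria item 8 reads "If patients are taking Riluzole and/or Radicava, they must be on a stable dose for at least thirty days prior to the baseline"; the remote-enrolment criteria repeat it. Background and Significance says "Radicava may slow disease progression in a subset of patients with a particular clinical presentation", and adds that more data are needed for ALS patients in general. Results of Open Label Trial says of earlier placebo-controlled studies that "patients on Riluzole, or on no therapy, lose on average -0.9 ALSFRS-R points per month", and the Figure 5 legend describes the pilot's historical controls as on Riluzole. Neither Statistical Methods nor Statistical Power states the background therapy or enrolment years of the 715.

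**The concern.** A criterion that allows a drug without requiring it is met equally by users and non-users. Selecting historical patients on it therefore does nothing to equalise Radicava use.

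In the combined fit all 60 memantine patients carry the trial's share of Radicava users, but only 30 of up to 745 controls do. If the historical set has less Radicava use and the drug slows decline, the pooled control slope is too steep for the trial's background, and the difference appears as a memantine effect. The only safeguard is the source test, and its sensitivity is limited by the 30 concurrent patients.

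The combined test is a planned efficacy test with its own power claim (over 90%), and Aim 2 would use a positive study to justify a larger trial.

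**Working it through.** **Inputs from the documents.** Historical placebo slope -0.89 points/month, 95% CI -0.95 to -0.83, n = 415 (Results of Open Label Trial); 60 and 30 randomised; up to 715 historical; 40% effect = 0.40 × 0.89 = 0.356; treatment test 10% two-sided; source test 5% two-sided.

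**Assumed.** Radicava uptake in the trial and slowing among users, neither of which is given; no Radicava in the pool; no memantine effect; equal slope SD in all groups. Only the product b = uptake × slowing matters for the bias.

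**Reproducing the plan's power.** SD = (0.06/1.96) × √415 = 0.624. Trial-only SE = 0.624 × √(1/60 + 1/30) = 0.140. Power = Φ(0.356/SE − 1.645) = 81.8%, against 82% stated. Combined SE = 0.624 × √(1/60 + 1/745) = 0.084; power is 99.5% given pooling, and 0.95 × 99.5% = 94.6% for passing the source test and then rejecting. Both agree with the stated figure of over 90%.

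**Share credited to memantine.** The background shift is 0.89b in both trial arms and zero in the pool. The bias is 0.89b × H/(H + 30): 715/745 = 96% of the shift with all 715, and 100/130 = 77% if only 100 qualify.

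**Source test.** SE = 0.624 × √(1/30 + 1/715) = 0.116. At b = 10% the shift is 0.089, and 0.089/0.116 = 0.77. It goes undetected with probability Φ(1.96 − 0.77) − Φ(−1.96 − 0.77) = 88%. At b = 20% it is still missed 67% of the time.

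**Error of the combined test.** With equal variances the source contrast and the pooled control mean are uncorrelated, so the rate given pooling has a closed form. With m = bias/0.084, it is Φ(m − 1.645) + Φ(−m − 1.645). The per-trial column is the pooling rate times the 715-control error.

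| Uptake × slowing | b | Pooling proceeds | Error given pooling, 715 | Per trial | Error given pooling, 100 |
|---|---|---|---|---|---|
| none | 0% | 95% | 10% | 10% | 10% |
| 30% × 10% | 3% | 94% | 12% | 11% | 11% |
| 50% × 10% | 5% | 93% | 14% | 13% | 12% |
| 30% × 20% | 6% | 93% | 16% | 15% | 13% |
| 30% × 30% | 9% | 89% | 24% | 21% | 17% |
| 50% × 20% | 10% | 88% | 27% | 24% | 18% |
| 50% × 30% | 15% | 79% | 46% | 36% | 28% |

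Simulation of the same scenarios agrees within about two points. From b = 9% upward with 715 controls, almost all rejections favour memantine. The randomised-only test stays at 10% throughout.

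**Adding Radicava by time, no historical users.** The treatment contrast is then a weighted average of non-users and users. At 30% uptake, the information is 1/(1/42 + 1/736) + 1/(1/18 + 1/9) = 39.7 + 6.0, giving SE = 0.624/√45.7 = 0.092. At 50% it is 1/(1/30 + 1/730) + 1/(1/30 + 1/15) = 28.8 + 10.0, giving SE about 0.100 (0.101 by simulation). In simulation with Radicava use assigned at random, the adjusted error was 9-11%, and power for the 40% effect stayed at about 96-99% given pooling.

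**The case against.** Several stronger readings are tempting, and the documents do not support them.

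- *The plan says its historical controls had no Radicava.* It does not. The wording about Riluzole or no therapy concerns published studies, and the Figure 5 wording concerns the pilot's comparator; the pilot's model used 415 patients from 8 trials. The 715 are not characterised.
- *All Radicava slowing is credited to memantine.* The 30 concurrent placebo patients stay in the control group, and the source test sometimes cancels pooling (33% of the time at b = 20%). The share is most, not all.
- *The bias has a known direction and size.* Direction depends on lower use in the pool and on a real slowing, which the plan says only may occur, in a subset. At 10% slowing the error is only about 11-15%.
- *The 82% power is wrong.* A power of 78% or 74% (b = 5% or 10%) follows only if the slope SD is held fixed while the effect shrinks. If the SD shrinks in proportion, power stays at 81.8%. The plan also says openly that "We used data from our historical placebo to estimate power".
- *Adjustment removes the problem.* Radicava use is not randomised. If users' natural slope differs by 0.15/month, the adjusted error is 13-16% against 15-29% unadjusted. If users naturally decline 0.3/month faster, at 20% slowing it is 20% and 30% (30% and 50% uptake) against 16% and 27%, which is no gain. Those selection sizes are also assumptions.

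What stands: entry criteria do not align background therapy, the model ignores it, and the source test is too weak to protect the combined test.

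**Conclusion.** The point holds for the additional combined test only. If Radicava use is lower in the historical pool and the drug slows decline, 77-96% of the average slowing is attributed to memantine when pooling proceeds. Over assumed uptake of 30-50% and slowing of 10-30%, the nominal 10% error becomes about 12-46% with all 715 controls and 11-28% with 100.

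These figures rest on assumed uptake and effect, on inferred absence of Radicava in the pool, on an SD derived from the pilot report's interval, and on treating the mixed model as a comparison of mean slopes. A reader might infer that the trial's main result is compromised. It is not: Radicava is open to both randomised arms, so the 90-patient comparison is unbiased. The stated 82% reproduces and is not in question here. The change is worth making before unblinding because the confounder is recorded and the adjustment is cheap.

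**What to change.** In Statistical Methods:

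1. State the recorded Radicava and Riluzole use in the historical set, and the number meeting the entry criteria.
2. Add Radicava use by time and Riluzole by time to both the source test and the combined model. Take trial patients' use from the screening concomitant-medication record and code historical patients by recorded use.
3. Report the combined test with and without these terms.
4. State that, where no historical patient used Radicava, its coefficient mixes drug effect with selection of users. The combined result is therefore supportive, and the conclusion on efficacy rests on the randomised comparison.

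The trial needs no new visits, patients or data items. The SE of the combined test rises from about 0.084 to 0.092-0.101, still well below the trial-only 0.140. If the source test is fitted to placebo patients alone and the pool has no users, it then rests on the concurrent non-users: 21 of 30 at 30% uptake, with its SE rising from 0.116 to 0.624 × √(1/21 + 1/715) = 0.138. Residual selection bias may remain.

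### The combined historical-placebo test gives trial and historical patients one intercept, so a starting-score gap that survives the preliminary comparison can leak partly into the memantine slope, in either direction

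*Combined protocol and SAP*

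**What the plan says.** Section II.C, Statistical Methods, sets out a linear mixed model for the 90 randomised patients with "fixed effects for intercept, placebo slope (rate of decline of ALSFRS-R) and change in slope for those treated with Memantine". On the random part it says: "Random effects included are for individual patient variation in intercept, slope and random error at each time point". The covariance between patient intercept and slope is not described. The treatment test is on the change in slope: "Testing for significance is two-sided at a 10% level of significance".

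The section then describes a further test, in which patients from a historical placebo database of 715 join the 30 trial placebo patients. Historical patients must satisfy this trial's entry criteria, but "There will be no patient-by-patient matching". The two placebo groups are first compared, "using the same model with a term added to identify source: historical or contemporary". If they differ, the pooled test is dropped. Otherwise: "If the placebo control sets do not differ, the lme model described above will be fit to the combined data".

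The text does not say whether the source term acts on level, slope or both, or that it stays in the pooled fit. The level of the preliminary comparison, two-sided 0.05, appears only in the Statistical Power simulation.

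**The concern.** Among the 90 randomised patients, randomisation justifies a single intercept. In the pooled data, nothing makes the mean starting scores of trial and historical patients equal. The Eligibility section requires ALSFRS-R above 25 and sets no upper limit, so two groups can meet the same criteria and still differ by points on average. Historical patients may be most of the pooled sample (up to 715 of 805), so they largely fix the common intercept. If trial patients start elsewhere, the fit reconciles the mismatch partly through the slope terms.

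The plan's power simulation could not show this. It draws the simulated trial patients and the remaining historical patients from one database, so their starting scores agree apart from sampling error.

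At stake is the 10% level of the combined test. A false slope effect could create or hide an apparent benefit of memantine even if placebo decline were identical in both sources.

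**Working it through.** **Inputs from the documents.** Placebo slope -0.89 points/month, 95% CI -0.95 to -0.83, from 415 patients (Results of Open Label Trial). Per-patient slope SD = (0.12/3.92) × √415 = 0.624, variance 0.389. Groups: 60 memantine, 30 placebo, up to 715 historical. Design effect 40% × 0.89 = 0.356.

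**Assumed, not in the documents.** Ten scores 28 days apart in both sources, no dropout, residual SD 2, intercept SD 4 to 5.5, intercept-slope correlation -0.2 to 0.4, starting gap d of 1 to 3 points, all 715 patients eligible.

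**The plan's own figures.** Trial only: SE = 0.624 × √(1/30 + 1/60) = 0.139; 0.356/0.139 = 2.55; power = Φ(2.55 - 1.645) = 81.8%, against the stated 82%. Combined: SE = 0.624 × √(1/60 + 1/745) = 0.0837; power 99.5%, times 0.95 for passing the preliminary comparison = 94.6%, consistent with the stated figure of over 90%.

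**The leak.** With balanced visits, the common-intercept fit is equivalent to regressing each patient's fitted slope on treatment and on that patient's fitted intercept. Direct mixed-model fits gave the same treatment estimates to four decimals. With equal true slopes and no drug effect,

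bias = -g × d × 715/745, where g = cov(intercept, slope)/var(intercept) of the per-patient estimates.

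Example with intercept SD 5.5, correlation 0.4, trial patients 3 points higher:
- Sampling error of the per-patient estimates adds 1.382 to the intercept variance, -0.237 to the covariance and 0.057 to the slope variance. The random-slope SD is √(0.389 - 0.057) = 0.576.
- var(intercept) = 5.5² + 1.382 = 31.63. Covariance = 0.4 × 5.5 × 0.576 - 0.237 = 1.030. g = 0.0326.
- Bias = -0.0326 × 3 × 0.960 = -0.094 points/month, 26% of the design effect and against memantine.
- SE = √(0.389 - 1.030²/31.63) × √(1/60 + 1/745) = 0.0800. The ratio is 1.17, and the two-sided 10% test rejects 32% of the time.

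At correlation -0.2 the same gap gives +0.079, in favour of memantine. At correlation 0 it gives +0.022; this is not exactly zero because of the -0.237 sampling covariance.

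Rejection rates before the preliminary comparison, equal slopes, no drug effect:

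| Intercept SD | Gap | corr -0.2 | 0 | 0.2 | 0.4 |
|---|---|---|---|---|---|
| 5.5 | 1 | 12% | 10% | 10% | 13% |
| 5.5 | 2 | 17% | 10.5% | 11% | 20% |
| 5.5 | 3 | 26% | 11% | 13% | 32% |
| 4 | 1 | 14% | 10% | 10% | 14% |
| 4 | 2 | 25% | 12% | 12% | 24% |
| 4 | 3 | 42% | 14% | 13% | 41% |

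With 200 historical patients instead of 715 and a 3-point gap, simulated rates were 11-32%.

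**What the preliminary comparison stops.**
- *Level term only.* At intercept SD 5.5 and correlation 0, the SE of the level difference is about 5.61 × √(1/30 + 1/715) = 1.05. A 2-point gap gives 1.91, so it is stopped 48% of the time. Over the correlations, 48-51% of 2-point and 82-85% of 3-point gaps are stopped; at intercept SD 4 the figures are 73-76% and 97-98%. Among 2-point cases that pass, simulated false-positive rates at intercept SD 5 were 10-21%. This term detects a true slope difference of 0.33 only 5-14% of the time.
- *Slope term only.* With a common intercept, the apparent slope difference is g × d. In the example this is 0.098 with SE 0.111, so 14% are stopped. About 85-95% of 3-point gaps pass at intercept SD 5 to 5.5, and 81-94% at SD 4.

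**With a source intercept.** The bias is zero under equal slopes and the level is 10% (9-12% in simulation). In the example the SE goes from 0.0800 to 0.0823. Combined power at the design effect stays about 94-95% after the preliminary comparison.

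**The case against.** The strongest reply is that a common intercept acts as a baseline adjustment. The plan requires only that the placebo groups do not differ; it does not say that equal slope alone is the condition. If decline depends on starting score, so that patients with the same true starting level decline alike in both sources, the plan's model is nearly right and the source intercept is the biased choice. At 3 points and intercept SD 5.5, rejection is then 10.9/11.1/11.4/11.9% with one intercept and 18.5/10.0/18.6/41.1% with two, for correlation -0.2/0/0.2/0.4.

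These figures reproduce, but in that setting the placebo groups differ in slope as well as level. At correlation 0.4 the slope difference is 3 × 0.4 × 0.576/5.5 = 0.126. The plan's rule is then not to pool. Unequal starts with equal slopes, by contrast, satisfy the rule if the source term is a slope term. Part of the reply stands, because the rule would rarely catch this. A source-by-time test with 30 trial placebo patients has SE 0.624 × √(1/30 + 1/715) = 0.116, and power of only about 19% against 0.126. Neither model is safe under both assumptions, so both fits should be shown.

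Two further points stand. Nothing in the documents indicates that a 2- or 3-point gap exists. And a level-term comparison, which the wording allows, would keep overall false-positive combined results at or below about 10%.

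**Conclusion.** The point holds as a limited weakness of the supplementary test. As written, the combined fit has one intercept and no source term, so a starting-score gap that passes the preliminary comparison can bias the memantine slope even when placebo slopes are equal. On the assumed values, the 3-point bias runs from about 0.02 to 0.12 points per month, or 6% to 33% of the design effect. Its size and sign rest on the covariance, the gap and the SDs, none of which the documents give.

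A reader might infer that any starting difference becomes a memantine effect, that the combined test leans towards memantine, or that the trial's main result is compromised. The documents support none of these. Random intercepts absorb most of a gap, the direction can go either way, and the primary comparison uses only the randomised patients.

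**What to change.** In Statistical Methods, before unblinding:
- Keep a source-specific intercept (trial or historical) in the combined model, and state the covariance structure of the random intercept and slope.
- Put both a source term and a source-by-time term in the preliminary comparison. Use source-by-time as the test of equal progression. Also check and report the level difference, with its confidence interval, rather than leaving it unexamined.
- Report the common-intercept combined fit as a sensitivity analysis, because the source-intercept fit relies on equal placebo slopes and can itself be biased if decline depends on starting score.
- Leave the 90-patient primary model as it is.

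The cost is one extra fixed effect, a few sentences of text, and an SE increase for the combined test of about 3% in the worked example and a few percent at most.
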